1.0 Study Summary

Study Title	Aerobic Exercise: A Potential Rescue from the Negative Repercussions of Poor Sleep
Study Design	Randomized, crossover
Primary Objective	To differentiate the effects of a multi-day partial sleep deprivation intervention on central hemodynamics in individuals with high vs low cardiorespiratory fitness.
Secondary Objective(s)	
To differentiate the effects of a multi-day partial sleep deprivation intervention on performance in individuals with high vs low cardiorespiratory fitness.
 
To differentiate the effects of a multi-day partial sleep deprivation intervention on overall health in individuals with high vs low cardiorespiratory fitness.

Research Intervention(s)/ Investigational Agent(s)	
1) 30% restriction in total sleep time for 4 days
 
2) 0% restriction in total sleep time for 4 days

IND/IDE #	N/A
Study Population	Men and women (age 18-39)
Sample Size	30
Study Duration for individual participants	~1.5 months
Study Specific Abbreviations/ Definitions	
Heart rate (HR): the frequency of heart beats over a given time (usually one minute)
 
Resting heart rate (RHR): the frequency of heart beats over a given time (usually one minute) measured at rest
 
Heart rate variability (HRV): term encompassing the time variation between successive heart beats over a given time (usually 5-10 minutes)
 
Interleukin (IL): specialized group of cytokines (i.e., protein); in this paper, the interleukins referenced will be those that are produced and released in response to inflammatory stimuli
 
Rating of Perceived Exertion (RPE): self-perceived measure of effort required from a task

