2.0 Objectives

Purpose

The purpose of the proposed study is to differentiate the effects of a multi-day partial sleep deprivation intervention on markers of central hemodynamics, cardio-autonomic function, physical and cognitive performance, as well as overall health in individuals with high vs low cardiorespiratory fitness (CRF). The proposed study would further elucidate the role that CRF plays in the repercussions of poor/insufficient sleep – a homeostatic disruption that is becoming more and more common place in today's age. Delineating this role would ultimately allow for a better understanding of potential factors that can be used to mitigate the deleterious effects of poor/insufficient sleep.

Aims/Hypotheses

Aim 1: To differentiate the effects of a multi-day partial sleep deprivation intervention on central hemodynamics (i.e., central blood pressure and arterial stiffness) in individuals with high vs low CRF.

Hypothesis: Individuals with higher CRF will exhibit a blunted response to the restricted sleep intervention (i.e., lesser increase in both blood pressure and arterial stiffness).

To accomplish Aim 1, we will assess central hemodynamics in individuals with high (i.e., $\geq 75^{\text{th}}$ percentile) and low ($\leq 25^{\text{th}}$ percentile) CRF (i.e., maximum oxygen consumption capacity [VO₂max]; determined via maximal treadmill testing) following 4 days of normal sleep and 4 days of partially deprived sleep.

Aim 2: To differentiate the effects of a multi-day partial sleep deprivation intervention on overall health (i.e., cardio-autonomic function and serum cytokine levels) and well-being (i.e., psychological mood states) in individuals with high vs low CRF.

Hypothesis: Individuals with higher CRF will exhibit a blunted response to the restricted sleep intervention (i.e., lesser augmentation of cardio-autonomic function, smaller increase in pro-inflammatory cytokines and decrease in anti-inflammatory cytokines, and lesser deviation in mood states).

To accomplish Aim 2, we will assess cardio-autonomic function (i.e., heart rate variability [HRV], resting heart rate [RHR], and recovery score), serum pro- (C-reactive protein [CRP], interleukin-6 [IL-6], IL-1 β , and tumor necrosis factor- α [TNF- α]) and anti-inflammatory (IL-10) cytokines, and psychological mood states in individuals with high and low CRF following 4 days of normal sleep and 4 days of partially deprived sleep.

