4.0 Study Endpoints

- 4.1 The primary and secondary study endpoints are as follows:
 - Do individuals with higher CRF exhibit differing central hemodynamic responses to acute partial sleep deprivation compared to individuals with lower CRF.
 - Do individuals with higher CRF exhibit differing central cardio-autonomic function responses to acute partial sleep deprivation compared to individuals with lower CRF.
 - Do individuals with higher CRF exhibit differing central serum cytokine responses to acute partial sleep deprivation compared to individuals with lower CRF.
 - Do individuals with higher CRF exhibit differing central psychological mood state responses to acute partial sleep deprivation compared to individuals with lower CRF.

- Do individuals with higher CRF exhibit differing central RSI responses to acute partial sleep deprivation compared to individuals with lower CRF.
- Do individuals with higher CRF exhibit differing central PVT responses to acute partial sleep deprivation compared to individuals with lower CRF.

4.2 *Describe any primary or secondary safety endpoints.*

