approximate time of day for each individual to account for diurnal patterns in the data collected. In total, the protocol will last approximately 5 weeks and consist of 5 visits.

Central Hemodynamic Assessment: Participants will be assessed for central arterial pulse wave form and cf-PWV following both sleep interventions with re-analysis occurring 3 days later to quantify the response to, and recovery from, the two sleep interventions between the two groups. The central hemodynamic (i.e., central blood pressure, augmentation index [absolute and relative to a heart rate of 75 beats per minute], mean arterial pressure, and pulse pressure) and arterial stiffness (i.e., cf-PWV) variables of interest will be collected and analyzed following methods identical to those utilized by Grosicki, et al. (34).

Health and Well-Being Assessment: Both metrics of sleep quality and cardio-autonomic function (i.e., resting heart rate, heart rate variability, and a proprietary, WHOOP-generated recovery score) will be collected via the WHOOP devices. The wearing of the device throughout the entirety of the project timeline will allow for the quantification of these measures in response to, and recovery from, the two sleep interventions, which will be compared between the two groups. Further, data from the devices will be analyzed following protocols set forth by Greenwalt, et al. (44). Using blood samples collected during the venipuncture protocols performed at the four data collection visits, sleep intervention response and recovery levels of circulating plasma concentrations of pro- (CRP, IL-6, IL-1 β , and TNF- α) and anti-inflammatory (IL-10) cytokines will be assessed using protocols similar to that outlined by Smith, et al. (45). Additionally, portions of the blood samples will undergo hematologic analysis to characterize shifts in the composition of immune cells through methods similar to those of Schluter et al. (46). Finally, POMS data will be used to evaluate intervention-associated shifts in psychological mood states between the two groups following the methodology of Shacham (47).

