16.2 N/A

17.0 Data Management and Confidentiality

17.1

Sample Size Estimation

Sample size requirements were determined via a priori power analyses using G*Power software (Ver. 3.1.9.4; Heinrich-Heine-Universität Düsseldorf, Düsseldorf, Germany) to ensure sufficient statistical power. To inform the expected effect size, we referenced Sunbul, et al. (49) who reported significantly higher wave velocity (PWV) values (5.33 ± 0.46 m/s) following one night of total sleep deprivation compared to one night of normal sleep (5.15 ± 0.26 m/s; $p=0.001$) in young, healthy males and females. Acknowledging that this will consist of an acute partial sleep deprivation intervention, a Cohen's f value of 0.24 was used in conjunction with an α level of 0.05, power of 0.80, with 2 groups (crossover design; 4 measures each), and a conservative correlation among repeated measured of 0.5. This resulted in a sample size estimate of 24 participants. The planned sample size was then increased based on the differences between the current study, the previous work, and the assessment of several secondary outcomes, as well as to account for expected attrition (~20%). Therefore, 30 participants will be recruited to maximize statistical power and account for expected attrition.

Statistics

Data will be presented as means \pm SD if normally distributed and assessed for normality via a Shapiro-Wilk Test. Assuming normality, all variables will undergo null-hypothesis testing with the α level set to 0.05. In the case that normality is violated, the appropriate non-parametric alternatives will be utilized. Analyses will be conducted using SPSS version 29.0 (SPSS, Inc., Chicago, IL).

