Analysis of Variance: Central hemodynamic and arterial stiffness variables will be interpreted using a mixed-model (i.e., within-between) repeated measures analysis of variance (RMANOVA) to identify interactions between multiple groups and conditions. Specifically, to test the hypothesis that individuals with higher CRF would demonstrate a blunted arterial stiffness response (i.e., maintained pulse transit times) to the acute partial sleep deprivation intervention, cf-PWV will be assessed following 4 consecutive nights of both normal sleep and restricted sleep and compared between the two groups. Likewise, all secondary variables will be assessed at pre-specified time points using a within-between interaction RMANOVA to test the hypotheses that individuals with higher CRF would demonstrate a blunted effect of partial sleep deprivation on markers of physical and cognitive performance (i.e., maintained RSI and PVT, respectively) as well as on markers of overall health (i.e., maintained cardio-autonomic function parameters, pro- and anti-inflammatory serum cytokine levels, and mood states).

In the case that sphericity is violated, a Greenhouse-Geisser correction will be performed. In the case of significance, a post hoc one-way ANOVA with Bonferroni tests will be used to identify significant differences. Effect sizes (ES) will be calculated by standardizing mean differences to the standard deviations (SD) of the placebo condition. Effect sizes will be qualified as follows: small $d = 0.2$, moderate $d = 0.5$, and large $d \geq 0.8$ (50).

17.2 The data will be kept secure through several routes. First, only the CITI certified research team will be allowed to be involved in the data collection process. Further, after acute bouts of data collection occur, all data will be collected together by the PI. If the data is physical, it will be kept in a locked drawer, behind a locked laboratory door. If the data is electronic, it will be kept on a password secured computer that only the PI may gain access. All human data will be coded, such that without the code it becomes unidentifiable.

17.3 Quality control of collected data will be ensured by controlling as many external variables as is reasonable. Further, biological measures (primary outcomes) will be measured in duplicate with the average of each measure used in the final assessment.

17.4 Describe how data or specimens will be handled study-wide:

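### cf-PWV is implied as the lead variable but never labelled primary, and six or seven central hemodynamic variables are each tested at 0.05 with no control across them

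*Combined protocol and SAP*

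**What the plan says.** **Objective and endpoints.** The primary objective in Section 1 is "To differentiate the effects of a multi-day partial sleep deprivation intervention on central hemodynamics in individuals with high vs low cardiorespiratory fitness". That is a domain, not a variable. Section 1 does place performance and overall health under secondary objectives. Section 4.1 then opens with "The primary and secondary study endpoints are as follows" and lists six questions, one per domain, without marking which is primary.

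**Aim 1.** The hypothesis in Section 2 is a "lesser increase in both blood pressure and arterial stiffness" in the fitter group. No rule says whether both are needed or either would do.

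**Variables.** Section 6.2 (Central Hemodynamic Assessment) lists "central blood pressure, augmentation index [absolute and relative to a heart rate of 75 beats per minute], mean arterial pressure, and pulse pressure", plus the "arterial stiffness (i.e., cf-PWV) variables of interest". Section 2 counts arterial stiffness as part of central hemodynamics; Sections 5.2 and 6.2 list it beside them.

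**Testing.** Section 17.1 states that "all variables will undergo null-hypothesis testing with the α level set to 0.05". Its Analysis of Variance text applies a within-between repeated measures ANOVA to the hemodynamic and stiffness variables, and singles out cf-PWV after each sleep condition as the test of the stiffness hypothesis. It then turns to the secondary variables, naming performance, cardio-autonomic, cytokine and mood measures. Central pressures and augmentation index are not in that list. The only multiplicity step is a Bonferroni post hoc test after a significant result.

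**Quality control.** Section 17.3 says "biological measures (primary outcomes) will be measured in duplicate", in the plural and without identifying them.

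**The concern.** The plan does not state which result decides Aim 1. Several central variables sit beside cf-PWV under the primary objective, each with its own test at 0.05, and the Bonferroni step works within a variable that is already significant, not across variables. If a significant interaction on any of them is reported as the Aim 1 finding, the error rate for the aim exceeds the nominal 5%. A reader of the results would also be unable to tell from the plan whether the variable that carries the conclusion was fixed in advance. On the narrower use of the term in Sections 5.2 and 6.2, the variable used for sizing falls outside the stated primary objective.

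**Working it through.** **1. The plan's own sizing (Section 17.1).** Inputs: pulse wave velocity 5.33 ± 0.46 against 5.15 ± 0.26 m/s; alpha 0.05; power 0.80; 2 groups; 4 measures; correlation 0.5; attrition about 20%.

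- d = (5.33 − 5.15) / √[(0.46² + 0.26²)/2] = 0.18 / 0.374 = 0.48, so f = d/2 = 0.24, as stated.
- Interaction test: λ = f²·N·m/(1 − ρ), with df = (m − 1) and (N − 2)(m − 1). At N = 24, λ = 0.0576 × 24 × 4 / 0.5 = 11.06 and power is 78.0%. N = 26 is needed for 80%; with f = 0.25, N = 24 is reached exactly. The stated 24 is reproduced to within two participants.
- 24 / (1 − 0.20) = 30, as stated.

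The sizing therefore allows for one test, on pulse wave velocity, at 0.05.

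**2. Number of tests.** Central blood pressure (1, or 2 if systolic and diastolic are separate), augmentation index (1), augmentation index at 75 bpm (1), mean arterial pressure (1), pulse pressure (1) and cf-PWV (1): six or seven.

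**3. Independence bound.**

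- Any direction: 1 − 0.95⁶ = 26.5%; 1 − 0.95⁷ = 30.2%.
- Protective direction only, 0.025 per test: 1 − 0.975⁶ = 14.1%; 1 − 0.975⁷ = 16.2%.

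**4. Correlated variables.** The documents give no correlations between variables, so a common correlation is assumed and varied. Simulation: 15 per group, no true effect, each variable tested by comparing the within-person difference between groups (two-sided 0.05, 28 df), 40,000 runs.

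| Assumed correlation | Any false interaction, 6 / 7 variables | Protective direction only, 6 / 7 variables |
|---|---|---|
| 0.3 | 24.5% / 27.1% | 12.6% / 13.7% |
| 0.5 | 21.3% / 23.5% | 10.9% / 11.8% |
| 0.7 | 16.8% / 18.1% | 8.5% / 9.0% |
| 0.9 | 10.9% / 11.4% | 5.5% / 5.6% |
| One test | 5% | 2.5% |

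**5. Built-in dependence.** A second simulation derived mean and pulse pressure from systolic and diastolic pressure. Assumed correlations were 0.6 between systolic and diastolic, 0.85 between the two augmentation indices, 0.4 between cf-PWV and each pressure, and 0.2 to 0.3 for the other pairs. It gave 21.6% / 22.4% for any false interaction and 11.1% / 11.6% in the protective direction, inside the range above.

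**6. Cost of adjusting across the set instead.** Bonferroni gives 0.05/6 = 0.0083 or 0.05/7 = 0.0071 per test. On the plan's sizing inputs, power per variable at N = 30 falls to about 67% or 66%, and 38 completers would be needed for 80%. One named primary variable keeps the test at 0.05.

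**The case against.** The strongest reply is that cf-PWV is already the primary endpoint in all but name. It is the sizing variable, and Section 17.1 describes its comparison between groups after the two sleep conditions before turning to the secondary variables. If cf-PWV alone decides Aim 1, the error rate is 5%. If the hypothesis requires both pressure and stiffness to be positive, an any-of-six calculation does not apply, although the choice among pressure variables would remain open. This reply stands in part: it shows that the lead variable is implied. It does not close the gap, because no section says so, the other central variables are not among the named secondary groups, and no decision rule accompanies the two-part hypothesis.

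Three stronger readings are tempting and not supported:

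- A reader might take 17–30% as the chance of falsely claiming that fitness protects. Those figures count interactions in either direction, and about half would show a worse response in the fit group. The 30% end also needs seven independent tests, which pulse pressure, mean pressure and two forms of augmentation index cannot supply.
- A reader might infer that the plan lets any one variable establish Aim 1. The documents do not say that; they leave the rule unstated.
- A reader might infer that a positive primary result is likely to be false. That needs a prior probability of a true effect, which the documents do not give.

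**Conclusion.** The point holds as a labelling and multiplicity gap. Followed as written, the plan tests six or seven overlapping variables under its primary objective at 0.05 each, with an implied but unlabelled lead. The chance of at least one false interaction is about 17–27% for assumed common correlations of 0.7 to 0.3. The independence bound is 26–30%, and the figure is about 11% at a correlation of 0.9. In the protective direction it is about 8–14%, against 2.5% for one test.

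These figures rest on the assumed correlations and on treating any significant variable as a finding for the aim. The split by direction is exact in expectation for the two-condition contrast. With four measures per person the interaction has 3 degrees of freedom, direction is settled only post hoc, and the split is approximate. The change is a cheap improvement worth making before the data are analysed.

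**What to change.** - In Sections 1, 4.1 and 17.1, state that the single primary endpoint is cf-PWV at the two immediate post-tests, tested by the group × condition interaction at 0.05.
- Label the other central hemodynamic variables as secondary. After cf-PWV, either test them in a pre-stated order or with a multiplicity adjustment, or report them as estimates with 95% confidence intervals and no confirmatory claim.
- Correct the reference to primary outcomes in Section 17.3 to match.

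The exact order of the secondaries, and a Holm adjustment for Aims 2 and 3, are optional.

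The cost is wording. Alpha and planned sample size do not change, since the trial was sized on pulse wave velocity at 0.05. The sizing assumes four measures per person whereas this contrast uses two; that mismatch already exists in Section 17.1 and is a separate matter that labelling neither creates nor resolves. The downside is that a result on augmentation index or a pressure variable alone could no longer be called the primary result.

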Experimental Visits: Following the first sleep intervention period, participants will come in for the first of four data collection visits (i.e., Post-Test 1). Data collection visits will begin of the completion of the Pittsburgh Sleep Quality Index (PSQI) and Profile of Mood States (POMS) questionnaire to characterize sleep quality and psychological mood states, respectively. Next, central arterial pulse wave form analysis and pulse transit time (carotid-femoral PWV [cf-PWV]; via applanation tonometry) will be assessed using a SphygmoCor XCEL device (AtCor Medical, New South Wales, Australia), followed by a standard venipuncture procedure to allow for inflammatory marker characterization, total blood cell counting, as well as blood lipid and glucose profiling to account for known hemodynamic confounders (26). The venipuncture procedure will be performed by the primary investigator (certified phlebotomist trained; 5+ years of experience) following the attached standard operating procedure for venipuncture and will entail the collection of 10-30 mL of blood, as is typical of a standard blood venipuncture procedure. If the primary investigator is unavailable to perform the procedure or is unable to do so, the Clinical Research and Trials Unit will be utilized. Lastly, participants will perform a short countermovement jump (CMJ) test to quantify their reactive strength index (RSI).

Participants will then undergo a 7-day washout/ post-intervention observation period, in which they will continue to track and log their sleep and perform daily PVT to allow for recovery evaluation in those metrics, prior to crossing over to the other sleep intervention. During the washout period, participants will also return to the lab to repeat the blood work and CMJ testing to allow for recovery assessment in those values (i.e., immediate post-intervention vs 3-day post-intervention values; Recovery 1). Following completion of the washout/observation period, participants will be assigned to the other sleep intervention in a crossover fashion and complete the second 4-day intervention before returning for another data collection visit (i.e., Post Test 2) identical to Post Test 1. They will then enter another 7-day post-intervention observation period and performing a second recovery data collection visit (i.e., Recovery 2). Data collection visits will occur at the same

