14.0 Withdrawal of Subjects

- 14.1* Subjects will be withdrawn from the research without their consent if they do not comply with prescribed bed and wake times for the entirety of either intervention.
- 14.2* Upon discovering the adherence problem, participants will be contacted via telephone or face-to-face and politely told they are disqualified from continuing the study due to adherence.
- 14.3* If participants withdraw of their own volition or are withdrawn by the PI, the research team will notify them via phone call or word of mouth in person. All data collected up until the point of withdrawal may be used at the PI's discretion for the results.

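### If the recovery visits enter the repeated measures ANOVA, one missed recovery reading removes a participant from the restricted-versus-normal comparison, and the sample size leaves no reserve for this

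*Combined protocol and SAP*

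**What the plan says.** Section 17.1 (Analysis of Variance) assigns central hemodynamics and arterial stiffness to a "mixed-model (i.e., within-between) repeated measures analysis of variance (RMANOVA") and adds that "all secondary variables will be assessed at pre-specified time points using a within-between interaction RMANOVA". Two details show that this is the classical ANOVA and not a likelihood-based mixed model: "In the case that sphericity is violated, a Greenhouse-Geisser correction will be performed", and the interpretation is built on within-between interactions. "Analyses will be conducted using SPSS version 29.0".

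The time points are called pre-specified but are not listed for any endpoint. The sample-size paragraph of Section 17.1 uses two groups with four measures each. It expects about 20% attrition and concludes: "Therefore, 30 participants will be recruited to maximize statistical power and account for expected attrition".

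Section 6.2 schedules Post-Test 1, Recovery 1, Post-Test 2 and Recovery 2. At the recovery visits participants "return to the lab to repeat the blood work and CMJ testing to allow for recovery assessment in those values". The Central Hemodynamic Assessment paragraph also repeats cf-PWV three days after each intervention. PVT and wearable readings are daily.

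On incomplete data, Section 14.1 says "Subjects will be withdrawn from the research without their consent if they do not comply with prescribed bed and wake times", and Section 14.3 leaves the use of data collected before withdrawal to the investigator's discretion. No section gives an analysis set, an imputation rule or any other missing-data method.

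**The concern.** A classical repeated measures ANOVA works on complete rows. A participant who lacks one level of the within-person factor leaves the whole analysis, including comparisons for which that participant has full data. In this design the question is whether the effect of restricted versus normal sleep differs by fitness group, and both post-tests are enough to answer it for a given person. If recovery readings are levels of the same ANOVA, a missed Recovery 2 blood draw discards an otherwise usable pair of post-tests.

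Two things are at stake. The first is precision, in a trial whose attrition allowance brings it back exactly to the calculated minimum. The second is that complete-case analysis is in general unbiased only when readings are missing completely at random, whereas one route to missing data here is failure to keep the prescribed sleep times.

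**Working it through.** **Inputs from Section 17.1:** f = 0.24, α = 0.05, target power 0.80, k = 2 groups, m = 4 measures, ρ = 0.5, N = 24 before attrition, attrition about 20%. The documents give no rate of missed visits, so 2%, 5% and 10% per visit are my assumptions.

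**1. The plan's own figure.** For the within-between interaction with sphericity, λ = f²·N·m/(1 − ρ), df1 = (k − 1)(m − 1), df2 = (N − k)(m − 1). At N = 24, λ = 0.0576 × 24 × 4 / 0.5 = 11.06, df1 = 3, df2 = 66, and power = 0.780. The smallest even N that reaches 0.80 is 26 (power 0.817). The stated 24 is therefore reproduced to within two participants, and only with four within-person levels.

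**2. The attrition allowance.** 24 / (1 − 0.20) = 30. If 20% of 30 leave, 24 remain, with no surplus for missed readings among those who stay.

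**3. Complete rows if all four visits are entered.** With an independent miss probability p per visit, the complete fraction is (1 − p)⁴. Power is from the formula in step 1.

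- p = 2%: 0.922 complete; 24 becomes 22.1; power 0.74
- p = 5%: 0.815 complete (18.5% deleted); 24 becomes 19.5; power 0.68
- p = 10%: 0.656 complete; 24 becomes 15.7; power 0.56

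If only the two recovery visits can be missed, the fraction is (1 − p)². Then 24 becomes 23.0, 21.7 or 19.4, with power 0.76, 0.73 or 0.67. If 30 people stay in the trial and p = 5%, 24.4 are complete and power is 0.79.

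**4. What using all readings recovers.** Simulation with 2 groups × 4 measures, f = 0.24, ρ = 0.5, readings missing completely at random, 2,000 runs. The all-readings analysis used participant effects and every available value.

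- 24 people, 5% missing: power 0.65 complete-case, 0.74 with all readings
- 24 people, 10% missing: 0.54 and 0.71
- 30 people, 5% missing: 0.79 and 0.85
- 30 people, 10% missing: 0.65 and 0.81

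These are powers for the four-level interaction, the test that the plan's calculation describes.

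**5. Standard error of the post-test group-by-condition contrast.** Generalised least squares, compound symmetry with ρ = 0.5 or 0.7, 24 complete participants plus 6 incomplete. The ratio is complete-case SE to all-data SE.

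- The 6 miss one recovery visit but have both post-tests: √(30/24) = 1.118
- The 6 drop out after Recovery 1 or after Post-Test 1: 1.02 to 1.04

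The 12% gain therefore belongs to missed recovery visits among people who stay. For true dropout, which is what the 20% in the plan describes, the gain is 2–4%.

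**6. Check on the replacement model.** With 30 people, complete data, and assumed correlations of 0.7–0.8 within a period and 0.3–0.5 across periods, a model with only a random participant intercept gave a type I error of 7–9% for the post-test contrast, against a nominal level "level set to 0.05". A paired-difference test held about 5%.

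**The case against.** The strongest reply is that the loss depends on which levels are entered. Section 17.1 describes the cf-PWV test as a comparison after normal and restricted sleep, and Section 2.0 frames Aims 2 and 3 in the same way. Recovery visits have their own stated purpose, which is immediate versus three-day values. On that two-level reading a missed recovery visit deletes nobody. This stands, and it is why the point is conditional. But the sample size of 24 was computed with four measures. With m = 2 in the same formula the smallest even N is 38, and power at 24 is 0.61. The reading that avoids the deletion is thus not the one on which the trial was sized, and the plan should say which applies.

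Second, attrition is already allowed for: 24 to 30 in Section 17.1, and up to 36 recruited for 30 completers in Section 12.2. For power against whole-person dropout this stands. It does not cover intermittent missed readings, except to the extent that 30 rather than 24 people actually finish.

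Third, Section 13.5 pays only for complete participation, and Section 6.2 lets those who deviate from the prescribed times restart, so missed visits may be rare. That is fair, and the 5% is only an assumption. Section 14.1 withdraws people for non-compliance where Section 6.2 has them restart. The two passages must be reconciled before anyone can say who ends up incomplete.

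A reader might infer three stronger things that the documents do not support:

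- That the expected 20% attrition costs 12% in standard error. The 12% needs all six people to miss only a recovery visit, a rate the plan does not give.
- That daily PVT or wearable readings would wipe out most of the sample. Over 22 daily values (4 + 7 days, twice) at 5% missing, 1 − 0.95²² = 68% would be deleted, but nothing in the plan makes each day a separate level.
- That loss differs by fitness group and biases the contrast. This is plausible, but no section shows it, and Section 14.1 applies to either intervention, not only to sleep restriction.

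Listwise deletion is a property of the named method and not a sentence in the plan. The non-parametric fallback in Section 17.1 offers no escape, because Friedman-type tests also need complete blocks.

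**Conclusion.** The concern holds in conditional form. If the four visits are the within-person levels, as the sample-size paragraph suggests, the planned ANOVA discards participants who have both post-tests. At an assumed 5% missing per visit about 19% are deleted; at 2% and 10% the figures are about 8% and 34%. Starting from the 24 left after expected attrition, power on the plan's inputs falls from 0.78 to between 0.74 and 0.56 over that range. If only the two post-tests are entered, a missed recovery visit costs nothing and the gain from partial data is limited to the 2–4% that applies to dropout.

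The results rest on independent misses, compound symmetry and, for the simulation, data missing completely at random. The point does not undermine the primary cf-PWV test as Section 17.1 words it. It should be fixed because the plan leaves the levels open, has no missing-data rule, and can use a better analysis of the same data at little cost.

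**What to change.** In Section 17.1:

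- List the time points entered for each endpoint.
- For each endpoint, make the primary test the group-by-condition contrast at the post-test, from a linear mixed model on all available data. Use REML with Kenward-Roger or Satterthwaite degrees of freedom, and fixed effects for group, condition, time (post, recovery), their interactions, period and sequence. Time drops out for outcomes measured only at the post-tests.
- Use an unstructured within-person covariance, or random participant and participant-by-period effects. A random intercept alone is not enough (step 6 of the working).
- Analyse recovery as a separate contrast.
- Summarise daily PVT and wearable values as the mean of available days in each 4-day block.
- Keep the complete-case RMANOVA as a sensitivity analysis, and replace the discretionary use of pre-withdrawal data in Section 14.3 with this rule.

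The cost is analysis wording, with the same data and software. The downsides are modest. The model assumes data are missing at random, and an unstructured covariance over four levels has 4 × 5 / 2 = 10 parameters to estimate from about 30 people; the participant-by-period form has fewer. The change does not remove bias if withdrawal for non-compliance depends on unobserved response. Withdrawals should therefore be reported by fitness group and condition, with reasons.
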